Appendix Table 1: Objective Response Status at Each Evaluation

Target Lesions	Non-target Disease	New Lesions	Objective status
CR	CR	No	CR
CR	Non-CR/Non-PD	No	PR
CR	Indeterminate or Missing	No	PR
PR	Non-CR/Non-PD, Indeterminate, or Missing	No	PR
SD	Non-CR/Non-PD, Indeterminate, or Missing	No	Stable
Indeterminate or Missing	Non-PD	No	Indeterminate
PD	Any	Yes or No	PD
Any	PD	Yes or No	PD
Any	Any	Yes	PD

If the protocol allows enrollment of patients with only non-target disease, the following table will be used:

Appendix Table 2: Objective Response Status at Each Evaluation for Subjects with Non-Target Disease Only

Non-target Disease	New Lesions	Objective status
CR	No	CR
Non-CR/Non-PD	No	Non-CR/Non-PD
Indeterminate	No	Indeterminate
Unequivocal progression	Yes or No	PD
Any	Yes	PD

20.3. The use of irRECIST (Immune-Related Response Evaluation Criteria in Solid Tumors) in this study

Throughout the study, subject management will be performed according to irRECIST (with the modification described below). irRECIST is based on the established RECIST (see Section 20.2) with changes that have been recommended as being better suited for assessing response to immunotherapeutic agents (Nishino, 2013; Bohnsack, 2014). irRECIST differs from conventional RECIST in that the development of new lesions is not automatically scored as PD, since atypical response patterns can occur. This reduces the risk of declaring a treatment to be ineffective based upon “pseudoprogression,” as has been well-documented for other immunotherapies (Hodi, 2016; Wolchok, 2009).

Blinded central reviewers will assess tumor response rates using irRECIST with modifications according to Appendix Table 3. In this study, irRECIST is modified as follows:

For purposes of determining progression based solely on worsening of non-target or new, non-measurable disease, “substantial, unequivocal worsening” requires confirmation by an additional scan (at least 4 weeks apart) unless it is accompanied by correlative symptoms.

Appendix Table 3: Objective Response using irRECIST

Response assessment	Description
irCR	
 • Complete disappearance of all lesions (and no new measurable or non-measurable lesions). • Pathological lymph nodes (target or non-target) must have diameter <10 mm in short axis. • Requires confirmation by consecutive assessment ≥ 4 weeks after first documentation.
irPR	
 • $\geq 30\%$ decrease in tumor burden from baseline. • No unequivocal progression of baseline non-target lesions. • No unequivocal progression of new, non-measurable lesions. • Requires confirmation by consecutive assessment ≥ 4 weeks after first documentation.
irSD	
 • Not meeting criteria for irCR or irPR, in absence of irPD.
irPD	
 • $\geq 20\%$ increase in tumor burden from nadir (the minimum recorded tumor burden). • The presence of new, measurable lesions does not define progression. New measurable lesions are added to the assessment of tumor burden. • A substantial, unequivocal worsening of baseline non-target lesions is indicative of irPD. • A substantial, unequivocal worsening of new, non-measurable lesions is indicative of irPD. • Requires confirmation by consecutive assessment ≥ 4 weeks after the first documentation.

irCR=immune-related complete response; irPD=immune-related progressive disease; irPR=immune-related partial response; irRECIST=Immune-related Response Evaluation Criteria in Solid Tumors; irSD=immune-related stable disease

## 1 MODIFICATION HISTORY

Version	Effective Date	Author(s) of Modification	Notes on Modification
1.0	15-NOV-2018	[name], Manager, Biostatistics, PROMETRIKA, LLC	
2.0	21-JUL-2020	[name], Senior Biostatistician, PROMETRIKA, LLC	
Revised description of the IDMC roles and responsibilities per updated Charter and Protocol v3.0.
 
Added Full Analysis Set to include subjects who are treated and have at least one post-baseline record collected. This analysis set will be used in the sensitivity analyses for ORR and OS.
 
“Modified irRECIST” was updated to “irRECIST” per Protocol v3.0.
 
Modified the stratified analysis approach to combine subjects from small strata instead of dropping subjects from the analysis.
 
Removed Modified ITT Population as no subjects will be dropped from the primary analysis.
 
Added Per Protocol Analysis Set as a sensitivity analysis of the primary endpoint family.
 
Added planned sensitivity analyses for OS.

Idera Pharmaceuticals, Inc.  
 Statistical Analysis Plan  
 Protocol Number: 2125-MEL-301

Version	Effective Date	Author(s) of Modification	Notes on Modification
2.0			
Removed interim analysis of OS
 
Updated the assumptions of the OS power calculations and changed the planned sample size per Protocol v4.0.
 
Added duration of response and PFS by blinded independent review as a secondary endpoint.
 
Modified analysis for injected and non-injected lesions to analyze at the subject level, create waterfall plots for responders only.
 
Added AE tables for subjects with organ-injected lesions
 
For QoL, it has been noted that some subjects has been using paper PRO instead of ePRO. Updated the corresponding analysis to run for paper PRO, and ePRO separately and combined as well. Removed QoL missing assessment analysis.
 
Remove summaries of irRECIST from all endpoints, and present irRECIST responses in a listing only.

Idera Pharmaceuticals, Inc.  
Statistical Analysis Plan  
Protocol Number: 2125-MEL-301

Version	Effective Date	Author(s) of Modification	Notes on Modification
3.0	22-JAN-2021	[name], Senior Biostatistician, PROMETRIKA, LLC	
Change OS analysis: HR will be generated using a Cox proportional hazards model instead of Pike estimator.
 
Clarify ORR definition and DOR censoring rule.
 
Update to include selected laboratory tests for shift analysis.
 
Add additional analyses for disease control rate, AE by injection status
 
Update date imputation rules to be consistent with other studies in the 2125 drug program
 
Add clarifications for the exposure summary

Idera Pharmaceuticals, Inc.  
 Statistical Analysis Plan  
 Protocol Number: 2125-MEL-301

---

## 2 LIST OF ABBREVIATIONS

Abbreviation	Definition
ADA	Anti-drug Antibody
ADaM	Analysis Data Model
AE	Adverse Event
ALT	Alanine aminotransferase
AST	Aspartate aminotransferase
ATC	Anatomical Therapeutic Chemical
BMI	Body Mass Index
CDISC	Clinical Data Interchange Standards Consortium
CI	Confidence Interval
CMH	Cochran-Mantel-Haenszel
CR	Complete Response
CSR	Clinical Study Report
CTCAE	Common Terminology Criteria for Adverse Events
CV	Coefficient of Variation
CYP	Cytochrome P450
DoR	Duration of Response
DRR	Durable Response Rate
ECG	Electrocardiogram
ECOG	Eastern Cooperative Oncology Group
eCRF	electronic Case Report Form
EORTC QLQ-C30	European Organisation for Research and Treatment of Cancer Quality of Life Questionnaire-Core 30
ePRO	Electronic Patient-Reported Outcome
FAS	Full Analysis Set
HR	Hazard Ratio
i.v.	Intravenous
IA	Interim Analysis
ICH	International Conference on Harmonisation
IDMC	Independent Data Monitoring Committee
irAE	Immune-related Adverse Event
irRECIST	Immune-related Response Evaluation Criteria in Solid Tumors
IRT	Interactive Response Technology
ITT	Intent to Treat
LDH	Lactate Dehydrogenase

Idera Pharmaceuticals, Inc.  
 Statistical Analysis Plan  
 Protocol Number: 2125-MEL-301

Abbreviation	Definition
LLN	Lower Limit of Normal
LLOQ	Lower Limit of Quantification
LS	Least Squares
MedDRA	Medical Dictionary for Medical Affairs
MMRM	Mixed Effect Model with Repeated Measures
NCI	National Cancer Institute
NE	Not Evaluable
ORR	Objective Response Rate
OS	Overall Survival
PD	Progressive Disease
PD-1	Programmed Cell Death-1
PFS	Progression-free Survival
PK	Pharmacokinetics
PR	Partial Response
PRO	Patient-reported Outcome
PT	Preferred Term
QoL	Quality of Life
QTcF	Fridericia's Corrected QT Interval
RECIST	Response Evaluation Criteria in Solid Tumors
SAP	Statistical Analysis Plan
SAE	Serious Adverse Event
SD	Stable Disease
SI	International System of Units
SLD	Sum of Longest Diameters
SOC	System Organ Class
TEAE	Treatment-emergent Adverse Event
TLF	Tables, Listings and Figures
TTR	Time to Response
ULN	Upper Limit of Normal
WHO	World Health Organization

Idera Pharmaceuticals, Inc.  
Statistical Analysis Plan  
Protocol Number: 2125-MEL-301

---

### **3 PURPOSE**

This statistical analysis plan (SAP) is written to incorporate the revisions from the protocol amendment v4.0 and provides a description of the planned statistical analyses of the study 2125-MEL-301 data to support the Clinical Study Report (CSR). Mock displays for tables, listings, and figures (TLF) are in separate supporting documents.

This SAP complies with the International Conference on Harmonisation (ICH) Harmonised Tripartite Guideline Topic E9, Statistical Principles for Clinical Trials. It is based upon the following study documents:

- Study Protocol v2.0 (dated 5 Feb 2018)
- Study Protocol v3.0 (dated 10 Jul 2019)
- Study Protocol v4.0 (dated 4 Jun 2020)

All decisions regarding the final analysis of the study data, as defined in this SAP, will be made prior to locking of the study data.

### **4 STUDY DESIGN**

This Phase 3 study is being performed to provide definitive evidence for superiority of the IMO-2125/ipilimumab combination over ipilimumab alone.

This is a randomized Phase 3 global, multi-center, open-label comparison of ipilimumab with and without intratumoral IMO-2125 in subjects with advanced melanoma who had confirmed disease progression during or after treatment with a programmed cell death-1 (PD-1) inhibitor, e.g., nivolumab or pembrolizumab. Confirmed progression is defined by irRECIST criteria. Subjects will be randomized 1:1 to ipilimumab alone or ipilimumab plus IMO-2125. Randomization is stratified on the duration of prior anti-PD-1 therapy ( $\geq 12$  weeks vs  $< 12$  weeks), metastasis stage (M1c vs other), and BRAF mutation status and prior targeted therapy (BRAF wild type, BRAF mutation positive with prior targeted therapy, or BRAF mutation positive with no prior targeted therapy) using block randomization. Targeted therapy is the use of an approved BRAF or MEK inhibitor alone or in combination. The primary endpoint family of the study comprises Objective Response Rate (ORR) and Overall Survival (OS) as evaluated by Response Evaluation Criteria in Solid Tumors (RECIST) v1.1.

Blinded independent review of all clinical and imaging results for response assessment will be performed centrally. Periodic safety reviews will be performed by an Independent Data Monitoring Committee (IDMC) as described in the IDMC Charter.

Idera Pharmaceuticals, Inc.  
 Statistical Analysis Plan  
 Protocol Number: 2125-MEL-301

Per protocol amendment v4.0, the planned interim analysis (IA) of OS will no longer be conducted, and the final analysis will occur when 392 randomized subjects have died or approximately 36 months after the last subject is randomized, whichever occurs first.

#### 4.1 OBJECTIVES AND ENDPOINTS

**Table 1: Study objectives and endpoints**

Objectives	Endpoints
Primary	
To compare the efficacy (measured by ORR and OS) of intratumoral IMO-2125 in combination with ipilimumab versus ipilimumab alone.	The primary endpoint family (see FDA Guidance for Industry, 2017) includes: 
 
• ORR by blinded independent review using RECIST v1.1
 
• OS
 

Secondary	

 
• To assess other measures of clinical benefit.
 
• To assess safety.
 
• To assess IMO-2125 pharmacokinetics (PK).
 
• To assess patient-reported outcomes (PROs) on quality of life (QoL).
 
	The secondary endpoints of this study are: 
 
• ORR by investigator assessment using RECIST v1.1
 
• Duration of response (DoR) by blinded independent review and investigator assessment using RECIST v1.1
 
• Durable response rate (DRR) by blinded independent review and investigator assessment using RECIST v1.1
 
• Time to response (TTR) by blinded independent review and investigator assessment using RECIST v1.1
 
• Progression-free survival (PFS), by blinded independent review and investigator assessment using RECIST v1.1
 
• Landmark PFS at 1 and 2 years, by blinded independent review and investigator assessment using RECIST v1.1 and landmark OS at 1 and 2 years
 

Idera Pharmaceuticals, Inc.  
 Statistical Analysis Plan  
 Protocol Number: 2125-MEL-301

Objectives	Endpoints
	
 
• Safety, including adverse events (AEs), laboratory and vital sign tests, electrocardiograms (ECGs), Eastern Cooperative Oncology Group (ECOG) Performance Status, and physical examination
 
• Plasma PK of IMO-2125
 
• PRO from the European Organisation for Research and Treatment of Cancer Quality of Life Questionnaire-Core 30 (EORTC QLQ-C30)
 

Exploratory	

 
• To investigate potential biomarkers.
 
• To investigate the incidence of anti-IMO-2125 and anti-ipilimumab antibodies.
 
	
The exploratory endpoints include:
 
 
• Immunologic biomarkers (optional tumor biopsies)
 
• Measurement of anti-IMO-2125 and anti-ipilimumab antibodies
 

## 4.2 PRIMARY STUDY HYPOTHESIS

ORR and OS comprise a primary endpoint family with a priori hypotheses to be tested. For ORR, the hypotheses are to demonstrate an increase in the ORR from the expected response of 12% for ipilimumab alone to 24% for the IMO-2125 + ipilimumab combination.

For OS, the hypotheses are to demonstrate improvement in the median survival from 11.40 months (the historical control for ipilimumab alone) to 16.85 months with the IMO-2125 + ipilimumab combination (hazard ratio [HR] = 0.677).

The corresponding hypotheses are:

$$H_0: HR = 1$$

versus

$$H_a: HR \leq 0.677$$

## 4.3 STUDY TREATMENTS

Ipilimumab will be administered intravenous (i.v.) using a 90-minute infusion duration at 3 mg/kg on Weeks 1, 4, 7, and 10 (ipilimumab alone or Weeks 2, 5, 8, and 11 (ipilimumab

Idera Pharmaceuticals, Inc.  
Statistical Analysis Plan  
Protocol Number: 2125-MEL-301

---

with IMO-2125). Cross-over therapy will not be allowed for subjects assigned to ipilimumab alone.

IMO-2125 will be given prior to ipilimumab on days when both are to be administered. IMO-2125, 8 mg will be administered intratumorally as a 1 to 4 mL injection to a single designated lesion at Weeks 1, 2, 3, 5, 8, 11, 16, 20, and 24.

#### **4.4 RANDOMIZATION PROCEDURES AND BLINDING**

This is an open-label trial. Randomization will use a central Interactive Response Technology (IRT) system. Subjects will be randomized in blocks of a 1:1 ratio to either ipilimumab with IMO-2125 or ipilimumab alone. Randomization is stratified by the duration of prior anti-PD-1 therapy ( $\geq 12$  weeks vs  $< 12$  weeks), metastasis stage (M1c vs other) and BRAF mutation (BRAF wild type vs BRAF mutation positive with prior targeted therapy vs BRAF mutation positive without prior targeted therapy). Despite this being an open label trial, the sponsor will make every effort to maintain the integrity of the trial by avoiding review of aggregated efficacy results by treatment arm during the course of the trial.

#### **4.5 DETERMINATION OF THE SAMPLE SIZE**

In this study, ORR and OS comprise a primary endpoint family; both have a priori hypotheses and will be tested for statistical significance. ORR will be tested first followed by OS. The fallback method for the primary endpoint family will be applied to control the study-wise Type I error rate. Under the fallback method,  $\alpha_1 = 0.02$  is assigned to the one-sided ORR test and an alpha of 0.005 is saved for the one-sided OS test. If the ORR test is significant at  $\alpha_1 = 0.02$ , this alpha is unused and will be passed to the OS test as an additional alpha of 0.02, giving a total alpha for the OS test of 0.025.

With 454 subjects planned with a 1:1 randomization ratio, this test will have 90% statistical power (calculated based on chi-square test) to demonstrate an increase in the ORR from the expected response of 12% for ipilimumab alone to 24% for the IMO-2125 + ipilimumab combination, at a 0.02 one-sided level of significance.

A sample size of 454 subjects also provides 90% power to test the alternative hypothesis of  $HR \leq 0.677$  at an  $\alpha$  of 0.005 (one-sided). The HR of 0.677 corresponds to an improvement in the median survival from 11.4 months (the historical control for ipilimumab alone) to 16.85 months with the IMO-2125 + ipilimumab combination. The number of required deaths to reach the 90% power is 392.

The OS power calculations are based on log-rank test and assume that the trial will have ~20 months of uniform accrual, an overall study duration up to 56 months, and a 10% drop-out rate. If a total alpha of 0.025 is available for the OS significance test under the fallback

Idera Pharmaceuticals, Inc.  
Statistical Analysis Plan  
Protocol Number: 2125-MEL-301

---

method, then this test will have 90% power to test the alternative hypothesis of  $HR \leq 0.72$  at an  $\alpha$  of 0.025 (one-sided). This corresponds to an improvement in the median survival from 11.4 months (the historical control for ipilimumab alone) to 15.8 months with the IMO-2125 + ipilimumab combination.

## **4.6 PLANNED INTERIM ANALYSIS AND SAFETY REVIEWS**

### **4.6.1 Interim Analysis of Overall Survival**

An interim analysis on the primary endpoint family efficacy measure of OS was planned to be performed at 50% of the required number of deaths in the earlier versions of the protocol. Per protocol version 4.0, the sponsor decided that this interim analysis will no longer be performed.

### **4.6.2 Interim Sample Size Re-estimation**

There is no sample size re-estimation planned for this study.

### **4.6.3 Independent Data Monitoring Committee Reviews**

The IDMC composition and duties are described in a separate Charter. The purpose of the IDMC is to provide independent evaluation of potential emerging risks to study participants, through ongoing evaluation of safety and clinical data contributing to an ongoing risk assessment of the study interventions, and make recommendations to the sponsor regarding the conduct of the study. Please reference the IDMC charter for timing of IDMC meetings.

## **5 CHANGES IN THE CONDUCT OF PLANNED ANALYSES**

There are no planned analyses that differ from those specified in the protocol.

## **6 STUDY ANALYSIS SETS**

### **6.1 SCREENED SET**

The Screened Set consists of all subjects who provided written informed consent and who undergo study screening procedures.

### **6.2 INTENT TO TREAT ANALYSIS SET**

The Intent to Treat (ITT) Analysis Set comprises all subjects in the Screened Set who were randomized. The ITT Analysis Set will be analyzed using the treatment to which the subject was randomized regardless of the treatment actually received and will be the primary analysis

Idera Pharmaceuticals, Inc.  
Statistical Analysis Plan  
Protocol Number: 2125-MEL-301

---

set for efficacy analyses. Any subject who receives a treatment randomization number will be considered to have been randomized.

### **6.3 FULL ANALYSIS SET**

The Full Analysis Set (FAS) comprises all subjects in the ITT Analysis Set who were treated with at least one dose of study drug, and had at least one post-baseline evaluable tumor assessment. The FAS will be analyzed using the treatment to which the subject was randomized regardless of the treatment actually received. Analysis of OS and ORR evaluated by RECIST v1.1 will be performed on the FAS as a sensitivity analysis.

### **6.4 PER PROTOCOL ANALYSIS SET**

The Per Protocol Analysis Set contains all subjects from the FAS without any exclusionary protocol deviations as defined in the Protocol Deviation Plan approved prior to database lock that could adversely affect the evaluation of the primary endpoint. In addition, subjects need to have at least three doses of IMO-2125 and two doses of ipilimumab for the combination arm and two doses of ipilimumab for the ipilimumab alone arm. Subjects will be analyzed according to their randomized treatment assignment. Analysis of OS and ORR evaluated by RECIST v1.1 will be performed on the Per Protocol Analysis Set as a sensitivity analysis.

### **6.5 SAFETY SET**

The Safety Set comprises all subjects in the ITT Analysis Set who received at least one dose of any study treatment. The Safety Set will be analyzed based on the actual treatment received.

### **6.6 PHARMACOKINETIC ANALYSIS SET**

The PK Analysis Set comprises all subjects who received at least one dose of IMO-2125 with at least one measurable concentration of IMO-2125.

## **7 GENERAL CONSIDERATIONS**

Analysis datasets will be created according to Clinical Data Interchange Standards Consortium (CDISC) standards, and data will be displayed according to reporting standards in this SAP and TLF formats.

SAS Version 9.4 or higher will be used to perform all data analyses and to generate tables, listings, and figures (TLFs).

All data collected in the database will be presented in data listings.

Idera Pharmaceuticals, Inc.  
Statistical Analysis Plan  
Protocol Number: 2125-MEL-301

---

For each subject, data up to the time of study completion, lost to follow-up, or withdrawal from study will be included in the appropriate analysis sets defined in [Section 6](#).

Continuous variables will be summarized in terms of the number of observations, mean, standard deviation, median, minimum, and maximum. Other descriptive statistics (e.g., quartiles, coefficient of variation) may be reported when appropriate. Categorical variables will be summarized using frequency counts and percentages. Analyses that use other descriptive statistics will be specified in the applicable SAP section.

Summaries will order displays by ipilimumab with IMO-2125 first, followed by the ipilimumab alone arm. Unless otherwise stated, summaries and figures will be reported by study arm. Summary statistics of central tendency will use one more decimal place than the collected data. Summary statistics of variability will use one more decimal place than the corresponding measure of central tendency. For example, the mean and median for age in years will be presented to one decimal place and the standard deviation of age will be reported to 2 decimal places. Percentages will be displayed to one decimal place, and proportions will be displayed to 4 decimal places. Durations for treatment exposure (weeks), adverse events (weeks), and response (months) will be displayed to 1 decimal place.

Planned visits will be used in all tables and figures that are by visit. Generally, only planned visits will be used in the summaries, statistical analyses, and calculations of any derived parameters; unscheduled visits will be included in the listings. However, both unscheduled and scheduled visits will be included in the determination of the worst-case (highest and/or lowest) post-baseline shifts for laboratory results, vital signs, and ECG.

All listings will include subject number and randomized treatment arm. The laboratory normal reference ranges will be provided and clinical laboratory test results outside the normal reference range will be flagged in the laboratory data listings.

Unless otherwise stated, all listings will be sorted by treatment arm, and subject number if appropriate, and then by visit date and time.

Deviations from the analyses pre-specified in this SAP will be identified in the CSR.

## **7.1 MULTICENTER STUDIES**

Data from all participating sites will be pooled for analysis.

## **7.2 MULTIPLE COMPARISONS AND MULTIPLICITY**

The Type I error rate will be adjusted for tests of both endpoints (ORR and OS) in the primary endpoint family. ORR will be tested first followed by OS. The fallback method for the primary endpoint family will be applied to control the study-wise Type I error rate.

Idera Pharmaceuticals, Inc.  
Statistical Analysis Plan  
Protocol Number: 2125-MEL-301

---

Under the fallback method,  $\alpha_1 = 0.02$  is assigned to the one-sided ORR test and an alpha of 0.005 is saved for the one-sided OS test.

- If the ORR test is significant at  $\alpha_1 = 0.02$ , this alpha is unused and will be passed to the OS test as an additional alpha of 0.02, giving a total alpha for the OS test of 0.025. The OS test will then be performed at the significance level of 0.025.
- If the ORR test is not significant at 0.02 level, then this alpha of 0.02 will not be available to be passed on for the OS test. The OS test will be performed at the originally reserved alpha of 0.005.

No further adjustment of the Type I error rate will occur. All analyses of secondary endpoints will be descriptive.

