15.4.1. Analysis of the Family of Primary Endpoints

15.4.1.1. Analysis of Objective Response Rate

The analysis of ORR (assessed by blinded independent review using RECIST v1.1) will be performed using a CMH test comparing the ORR for the two treatment groups controlling for the randomization strata. This is the only test of RECIST v1.1 ORR that will be done. The analysis of ORR will take place when all randomized subjects fall within one of the following categories:

- completed scheduled study treatment and completed at least 28 weeks on the study;
- prematurely discontinued study treatment and completed at least 28 weeks on the study;
- withdrew, were lost to follow-up, or died before completing at least 28 weeks on the study.

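### The one-way fallback between ORR and OS is valid, but never returning the OS alpha to ORR gives up about 0.5 to 1.4 points of ORR power that the 0.025 family-wise bound would allow

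*SAP*

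**What the plan says.** SAP 7.2 states the aim: "The fallback method for the primary endpoint family will be applied to control the study-wise Type I error rate". The order is fixed: "ORR will be tested first followed by OS". A level of 0.02 "is assigned to the one-sided ORR test and an alpha of 0.005 is saved for the one-sided OS test". If ORR is significant, its 0.02 is added to the OS level, "giving a total alpha for the OS test of 0.025". If ORR is not significant, "The OS test will be performed at the originally reserved alpha of 0.005".

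The section closes the procedure with "No further adjustment of the Type I error rate will occur", and secondary endpoints are descriptive. No branch covers ORR missing 0.02 and OS then succeeding at 0.005.

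The same one-way rule, in full or in part, stands in the Protocol synopsis, Protocol 15.1 and 15.4, and SAP 4.5 and 10.1.3. On the ORR test, Protocol 15.4.1.1 says "This is the only test of RECIST v1.1 ORR that will be done", and SAP 10.1.1 also makes it the sole ORR analysis.

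**The concern.** The plan treats the alpha of a rejected hypothesis as reusable, but only in the direction ORR to OS. When OS is rejected at its own 0.005, that 0.005 could be returned to ORR on the same logic, so that ORR would be judged at 0.005 + 0.02 = 0.025.

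As written, an ORR p-value in (0.02, 0.025] with an OS p-value of at most 0.005 leaves one of the two members of the primary endpoint family formally unproven. The study-wise limit that the plan sets itself does not require this. At stake is a formal ORR claim in a trial whose OS claim has already succeeded. The success of the trial as a whole is not at stake.

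**Working it through.** **Inputs.** From SAP 4.5: 454 subjects 1:1 (227 per arm), ORR 12% vs 24% at one-sided 0.02, and 392 deaths. OS HR is 0.677 at one-sided 0.005, or 0.72 at one-sided 0.025. From SAP 7.2: the alpha rule. The documents give no correlation between the ORR and OS test statistics, so 0 to 0.7 is assumed.

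**1. The plan's own figures reproduce.**
- ORR power = Φ{[0.12√227 − z√(2 × 0.18 × 0.82)] / √(0.12 × 0.88 + 0.24 × 0.76)}. At z = 2.054 (0.02) this is Φ[(1.808 − 1.116)/0.537] = Φ(1.290) = 90.1%. SAP 4.5 says "With 454 subjects planned with a 1:1 randomization ratio, this test will have 90% statistical power (calculated based on chi-square test").
- OS deaths = 4(2.576 + 1.282)² / (ln 0.677)² = 59.52/0.1522, which rounds up to 392.
- OS power with 392 deaths = Φ(½√392 × |ln HR| − z). At HR 0.677 and 0.005 this is Φ(3.862 − 2.576) = 90.1%. At HR 0.72 and 0.025 it is Φ(3.252 − 1.960) = 90.2%.
- Alpha: 0.02 + 0.005 = 0.025.

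**2. The two-way rule is valid.** Use closed testing. Reject the joint null if ORR p ≤ 0.02 or OS p ≤ 0.005; by Bonferroni its level is at most 0.025 at any correlation. Test each single null at 0.025. The result is:
- OS is rejected if p ≤ 0.005, or if p ≤ 0.025 with ORR p ≤ 0.02. This is exactly the present OS rule, so OS power is unchanged.
- ORR is rejected if p ≤ 0.02, or if p ≤ 0.025 with OS p ≤ 0.005. The second clause is the one the plan omits.

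Everything the present rule rejects is still rejected.

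**3. Error rates, one-way against two-way.**

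| True state | As written | With pass-back |
|---|---|---|
| Both nulls true, any rejection, correlation 0 | 1 − 0.98 × 0.995 = 0.0249 | 0.0249 |
| Both nulls true, any rejection, correlation 0.7 | 0.0226 | 0.0226 |
| Only OS null true, false OS claim | ≤ 0.025 | ≤ 0.025 |
| Only ORR null true, OS HR 0.677, false ORR claim | 0.020 | 0.0245 to 0.0250 |

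In the last row at correlation 0, the figure is 0.020 + 0.005 × 0.901 = 0.0245. It cannot exceed 0.025.

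**4. Power gained.** The gain is the probability that ORR p lies in (0.02, 0.025] and OS p ≤ 0.005. ORR power at 0.025 is 91.7%. Treating the ORR statistic as normal with the mean that gives 90.14% power at 0.02, the window has probability 0.9167 − 0.9014 = 0.0153. OS power at 0.005 is 0.901 (HR 0.677) or Φ(3.252 − 2.576) = 0.751 (HR 0.72). At correlation 0 the gains are 0.0153 × 0.901 = 0.0138 and 0.0153 × 0.751 = 0.0115. With bivariate normal statistics:

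| Correlation | Gain, HR 0.677 (points) | Gain, HR 0.72 (points) |
|---|---|---|
| 0 | 1.38 | 1.15 |
| 0.3 | 1.26 | 0.94 |
| 0.5 | 1.17 | 0.77 |
| 0.7 | 1.05 | 0.55 |

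ORR power therefore becomes 91.2% to 91.5% (HR 0.677) or 90.7% to 91.3% (HR 0.72).

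**5. What the window looks like.** By unstratified chi-square, 27 vs 42 responders of 227 gives z = 0.0661/0.0337 = 1.961, one-sided p = 0.0249. With 27 control responders, 41 is too few (p = 0.033) and 43 already passes 0.02 (p = 0.019).

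**The case against.** The strongest reply is that nothing is wrong with the plan. The fallback method is named, ordered and described consistently in both documents, and every design figure reproduces. Choosing it over a weighted Holm or graphical procedure is a legitimate design choice. That stands: this is an avoidable inefficiency, not a defect in error control.

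A reader might infer that the one-way rule buys no protection at all, or that pass-back is entirely free. The plan does not support that reading. If ORR is truly unaffected and OS truly improves, the present rule holds a false ORR claim to 0.020, and pass-back lets it approach 0.025. The equal error rates in the first two rows of the error table are automatic, because under the global null alpha is returned only after OS has already been falsely rejected. What remains true is that the family-wise rate, the only rate the plan undertakes to control, keeps the same bound.

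The practical value is also limited. The ORR analysis waits until all subjects have reached 28 weeks or left the study. OS comes at 392 deaths or about 36 months after the last randomization. If the time limit applies, the gap could be about 36 − 28 × 7/30.4375 = 29.6 months. A recovered ORR claim would arrive that late, and only when OS has already succeeded. Pass-back cannot rescue a trial that fails on OS.

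These are small, nameable costs. None of them gives a power or validity reason to prefer the one-way rule for the stated aim.

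**Conclusion.** The point holds as a low-priority improvement. The one-way fallback is valid at 0.025 one-sided, but the two-way version rejects everything it rejects and adds ORR rejections under the same family-wise bound. That conclusion needs no assumption about correlation.

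The size does depend on assumptions: the design ORR rates, 392 deaths, normal approximations, and a correlation of 0.7 down to 0. On these the gain in ORR power is about 1.1 to 1.4 points at OS HR 0.677 and 0.5 to 1.1 points at HR 0.72. If the time limit ends the study with fewer deaths, OS power at 0.005 falls and so does the gain. A claim that the plan fails to control Type I error, or that it loses material ORR power, would go beyond what the documents show.

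**What to change.** Add to SAP 7.2 and Protocol 15.4 a sentence to this effect: *If ORR is not significant at 0.02 but OS is significant at 0.005, the 0.005 is returned to ORR, and the p-value from the single planned ORR analysis is compared with 0.025; no second ORR test is performed on later data.* Align the Protocol synopsis and 15.1, and SAP 4.5 and 10.1.3.

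Two conditions matter. The change must be fixed before any ORR result by arm is known; the study is open-label, so this should be documented. The bar on a second test must be explicit, because SAP 16.2 schedules the ORR response table at both the ORR and the final analysis. A fresh test on final data would be a second look and would contradict Protocol 15.4.1.1 and SAP 10.1.1.

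The cost is a few lines in six places, plus a protocol amendment with the review and approval that Protocol 18.4 requires. No extra subjects, deaths or analyses are needed. If the sponsor prefers the stricter 0.020 for ORR alone, keeping the present rule is defensible, and one sentence giving that reason would suffice.
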